## MS-TAQ Modified Self-Injectables Version to assess adherence during last previous injectable DMD treatment

1.) Before enrolling in this study, what self-injectable medication were you taking to treat your Multiple Sclerosis (MS)? (Check one)

Avonex	
(interferon beta 1a intramuscular)	
Betaseron	
(interferon beta 1b subcutaneous)	
Copaxone (glatiramer acetate)	
Extavia (interferon beta 1b)	
Glatopa (glatiramer acetate)	
Plegridy (peginterferon beta 1a)	
Rebif (interferon beta 1a subcutaneous)	
Other, please specify:	

2.) During the last 4 weeks (28 days) that you were taking this medication, how many days were you supposed to take this medication? (Check one)

Every day (28 times)	
Every other day (14 times)	
Three times a week (12 times)	
Once a week (4 times)	
Once every two weeks (2 times)	
Other, please specify:	

3.) Did you miss or forget to take any doses of this medication during the last 4 weeks (28 days) that you were taking the medication? (Check one)

Yes	
No	

4.) How many doses did you miss or forget to take? (Complete blank)

# IF YOU HAVEN'T SKIPPED ANY DOSES IN THE PAST 28 DAYS, SKIP TO QUESTION 6

#### (Complete this section only if you missed a dose in the past 28 days)

5.) How important were the following factors in missing or forgetting to take a dose? (Please check one answer for each)

	Not important at all	A little important	Moderately important	Extremely important
Memory problems	0	1	2	3
Too busy	0	1	2	3
Side effects of injection	0	1	2	3
Fear of needles	0	1	2	3
Needing someone to help me take my medication	0	1	2	3
Ran out of medication or could not refill my prescription	0	1	2	3
Away from home and could not access my medication	0	1	2	3
Feeling anxious, depressed, or nervous about taking my medication	0	1	2	3
Dissatisfaction with my medication	0	1	2	3
Did not want taking my medication to interfere with activities	0	1	2	3
Tired of taking my medication	0	1	2	3
Did not feel like taking my medication	0	1	2	3

6.) Overall, how hard or easy do you feel it is to take your most recent Multiple Sclerosis treatment as recommended by your physician? (Check one)

Extremely easy	1
A little hard	2
Moderately hard	3
Very hard	4
Extremely hard	5

7.) Overall, how satisfied are you with how things have been with your treatment during the past 4 weeks (28 days)? (Check one)

Not satisfied at all	1
A little satisfied	2
Moderately satisfied	3
Very satisfied	4
Completely satisfied	5

#### MS-TAQ modified for cladribine tablets

1.) What treatment week of cladribine tablets did you most recently complete? (check one)

Year 1, Treatment Week 1	
Year 1, Treatment Week 2	
Year 2, Treatment Week 1	
Year 2, Treatment Week 2	
Other, please specify:	

2.) How many cladribine tablets were you supposed to take during this treatment week? (complete the blank)

3.) Did you miss or forget to take any cladribine tablets during this treatment week? (Check one)

Yes	
No	

4.) How many cladribine tablets did you miss or forget to take? (Complete blank)

## IF YOU HAVEN'T SKIPPED ANY DOSES IN THE PAST 28 DAYS, SKIP TO QUESTION 6

#### (Complete this section only if you missed a dose in the past 28 days)

5.) How important were the following factors in missing or forgetting to take a dose? (Please check one answer for each)

	Not important at all	A little important	Moderately important	Extremely important
Memory problems	0	1	2	3
Too busy	0	1	2	3
Side effects of medication	0	1	2	3
Ran out of medication or could not refill my prescription	0	1	2	3

	Not important at all	A little important	Moderately important	Extremely important
Away from home and could not access my medication	0	1	2	3
Feeling anxious, depressed, or nervous about taking my medication	0	1	2	3
Dissatisfaction with my medication	0	1	2	3
Did not want taking my medication to interfere with activities	0	1	2	3
Tired of taking my medication	0	1	2	3
Did not feel like taking my medication	0	1	2	3

6.) Overall, how hard or easy do you feel it is to take cladribine tablets as recommended by your physician during your treatment week? (Check one)

Extremely easy	1
A little hard	2
Moderately hard	3
Very hard	4
Extremely hard	5

7.) Overall, how satisfied are you with how things have been with your cladribine tablet treatment during your treatment week? (Check one)

Not satisfied at all	1
A little satisfied	2
Moderately satisfied	3
Very satisfied	4
Completely satisfied	5

#### SAS code for multiple imputation analysis (example)

The following SAS code is a reduced example that can be adapted for the analysis:

```
* aval is the ARR at month 24 ;
proc mi data=RELAPDATA out=ARRmiout nimpute=20 seed=123;
    class sex;
    fcs regpmm(blweight aval age);
    var age aval blweight sex;
run;
proc means data= ARRmiout N MEAN STD STDERR MIN MAX;
    by _Imputation_;
    var aval;
    output out=ARRmeans_imputed N=n MEAN=mean STD=std STDERR=stderr
MIN=min MAX=max;
run;
proc mianalyze data= ARRmeans_imputed;
    modeleffects mean;
    stderr stderr;
```

run;

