#### Significance level

When confidence intervals (CIs) are to be calculated, these will be two-sided with a confidence probability of 95%, unless otherwise specified in this IAP. For continuous data, CIs for the mean will be calculated assuming a normal distribution of the data. CIs for binary endpoints will be presented using the Clopper-Pearson method. All statistical tests mentioned in this IAP are to be regarded as exploratory. The significance level is 5% two-sided. If p-values are to be presented for descriptive purposes it will be indicated with the statement that no inferential conclusion should be drawn from the p-value.

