## 14 Efficacy Analyses

## 14.1 Primary Endpoint: ARR

## 14.1.1 Primary Objective: Analysis of the ARR

Analysis (Analysis	Derivation	Statistical Analysis Methods	Missing data handling
Population)			
Primary endp	oint: ARR over 24 Month	S	
Primary (FAS)	ARR over 24 Months. The ARR over 24 Months of a patient is calculated as the number of relapses of the patient divided by the number of days on study for that patient and multiplied by	The population estimate will be based on the average of the ARR values for the patients in the study. The corresponding 95% CI will be reported. The Statistical Analysis Software (SAS) ® MEANS procedure will be used to compute these quantities. The following descriptive statistics will be reported: mean,	Patients discontinuing early are analyzed according to number of years of follow-up on treatment and number of relapses observed at the time of discontinuation.
Secondary (PP)	365.25. This variable will be considered to get population estimates.	SD, min, max, median, first quartile (Q1) and third quartile (Q3).	
	A relapse will be defined as per routine clinical practice as determined by the investigator		
	Time on Study (days) = (Date of Study Completion or Date of study discontinuation - Date of first dose of cladribine tablets +1)		
Sensitivity (FAS)	Model based ARR, defined as expectation of relapses divided by time on study.	The estimate of the expected ARR at Month 24 will be based on a Negative Binomial (NB) model for relapse count, with offset equal to the log of years on study and adjustment for categorical number of relapses in the last 2 years, or since MS diagnosis if diagnosis <24 months (≤1 relapse, >1 relapse). The NB regression will be computed with the SAS ® GENMOD procedure, using the dist=NB option in the MODEL statement	Same handling as for the primary analysis

Analysis (Analysis Population)	Derivation	Statistical Analysis Methods	Missing data handling
		*The estimate of the expected ARR at Month 24 will be based on a Zero Inflated NB model for relapse count, with offset equal to the log of years on study and adjustment for categorical number of relapses in the last 2 years, or since MS diagnosis if diagnosis <24 months (≤1 relapse, >1 relapse). The NB regression will be computed with the SAS ® GENMOD procedure, using the dist=ZINB option in the MODEL statement.	

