## 14.1.4 Subgroup Analyses of ARR

The subgroup analyses of the primary endpoint (at Month 24 for the ARR during the follow-up period) will be conducted on the FAS population.

A subgroup analysis at Month 24 of the ARR during the follow-up period for patients completing the study and patients who drop out will be performed. Estimates and CIs for the 2 subgroups will be reported using the same method of the primary analysis.

The same analysis will be performed for patients completing the treatment and patients who do not complete the treatment (i.e., completing Year 1 treatment but not Year 2 treatment) when the number of patients in the last group is greater than 10.

A subgroup analysis at Month 24 of the ARR during the follow-up period will be performed with reference to the type of MS at screening (RRMS, aSPMS, PPMS and CIS).

For the primary outcome, the patterns of missingness will be explored. When the number of missing values is substantial (>5%), multiple imputation methodology will be considered for the analysis of the primary objective. At least 20 imputed datasets will be considered. The ARR at Month 24 for a patient will be considered missing if for that patient the number of relapses at Month 24 is missing or if the Time on Study for that patient is missing. At least the following variables will be considered in the imputation model:

- ARR at Month 24
- Type of MS at screening
- Number of relapses in the previous 2 years
- Age
- Sex
- Baseline Body Mass Index (BMI)
- Compliance

Since we have both continuous and categorical variables in the imputation model the Fully Conditional Specification method will be considered for the imputation. Predictive mean matching will be used for the imputation of the following variables: ARR at Month 24, number of relapses in the previous 2 years, age, baseline BMI and compliance. SAS code for the analysis is available in the appendices.

CCI

Cladribine CLICK-MS MS700568\_0078 Version 7.0

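### If the primary ARR is multiply imputed as in the SAP's example code, PROC MIANALYZE is given no complete-data degrees of freedom, so the pooled 95% CI is slightly too narrow in a small cohort

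*SAP*

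**What the plan says.** **Without imputation.** SAP 14.1.1 estimates the ARR as the average of the per-patient rates in the Full Analysis Set (FAS). For the estimate and its interval, the SAS "MEANS procedure will be used to compute these quantities". SAP 9 (Significance level) says of confidence intervals that "these will be two-sided with a confidence probability of 95" percent, and adds: "For continuous data, CIs for the mean will be calculated assuming a normal distribution of the data".

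**With imputation.** SAP 14.1.4 says that when more than 5% of values are missing, "multiple imputation methodology will be considered for the analysis of the primary objective". It adds that "At least 20 imputed datasets will be considered" and refers to the appendix for code. No rule is given for the degrees of freedom of the pooled interval.

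**The code.** The SAP 18 example imputes with "proc mi data=RELAPDATA out=ARRmiout nimpute=20 seed=123", runs PROC MEANS on each imputed data set, and pools with "proc mianalyze data= ARRmeans_imputed". The pooling statements are "modeleffects mean" and a line naming the standard error. There is no EDF= option. The listing is introduced as a cut-down example open to adaptation.

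**The concern.** The same estimand, a mean of per-patient rates, gets two different reference distributions depending on whether imputation is used. PROC MEANS allows for estimating the variance from N patients. The pooling step as written allows only for the finite number of imputations and ignores that each within-imputation variance also comes from N patients. When N is modest and little information is missing, the second source of uncertainty is the larger one.

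At stake is the width, and so the actual coverage, of the 95% CI reported with the primary estimate if imputation is used. The point estimate and the pooled standard error are unaffected.

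**Working it through.** The documents give no N, degrees of freedom or interval width for this analysis, so there is no planned figure to reproduce.

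**Inputs from the SAP**
- Two-sided 95% interval (SAP 9).
- m = 20 imputations (SAP 18 code; SAP 14.1.4 says at least 20).
- No complete-data degrees of freedom passed to the pooling step (SAP 18 code).

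**Assumptions**
- N: 30 to 300. The study-size section is not in the text available. The first interim analysis uses the first 30 patients enrolled, so 30 is about the floor.
- Fraction of missing information λ: 0.06 to 0.20, with 0.30 and 0.50 as stress cases.
- Standard software behaviour, not stated in the documents: PROC MEANS limits use t with N-1 degrees of freedom, and EDF defaults to infinity in PROC MIANALYZE.

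**Formulas**
- As coded (Rubin, large sample): ν = (m-1)/λ².
- With EDF = v0 = N-1 (Barnard-Rubin): ν_obs = ((v0+1)/(v0+3)) × v0 × (1-λ), and ν_adj = 1/(1/ν + 1/ν_obs).
- At a given pooled standard error, width is proportional to the critical value, so the shortfall is 1 - t(ν)/t(ν_adj).

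**As coded.** ν = 19/λ² is 5,278, 1,900 and 475 at λ = 0.06, 0.10 and 0.20. The critical values are 1.960, 1.961 and 1.965, whatever N is. At λ = 0.30, ν = 211 and the value is 1.971.

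**Worked example, N = 40, λ = 0.10.** ν_obs = (40/42) × 39 × 0.90 = 33.4. ν_adj = 1/(1/1,900 + 1/33.4) = 32.9, with critical value 2.035. Shortfall: 1 - 1.961/2.035 = 3.6%.

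| N | t(N-1) | Adjusted critical value, λ = 0.06 to 0.20 | Coded interval too narrow by |
|---|---|---|---|
| 30 | 2.045 | 2.058 to 2.081 | 4.7-5.6% |
| 40 | 2.023 | 2.031 to 2.049 | 3.5-4.1% |
| 80 | 1.990 | 1.994 to 2.004 | 1.7-2.0% |
| 100 | 1.984 | 1.987 to 1.996 | 1.3-1.6% |
| 150 | 1.976 | 1.978 to 1.985 | 0.9-1.0% |
| 200 | 1.972 | 1.973 to 1.980 | 0.7-0.8% |
| 300 | 1.968 | 1.969 to 1.975 | 0.4-0.5% |

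If the adjusted t distribution is right, the coded interval's coverage at λ = 0.10 is 93.9% at N=30, 94.2% at N=40, 94.6% at N=80, 94.7% at N=100 and 94.8% at N=200.

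**Simulation.** There were 4,000 runs per setting, with 10% or 20% missing completely at random, m = 20 and N = 31, 50 or 100. Imputation used simple proper or bootstrap draws, not the plan's predictive mean matching.
- Normal data: the coded interval covered 0.3 to 1.3 points less than the adjusted one.
- Skewed counts (negative binomial, assumed mean ARR 0.2), N=50, 10% missing: 91.6% coded and 92.2% adjusted. The option recovers 0.6 points; the remaining 2.8 points below 95% are not due to the degrees of freedom.

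**The case against.** **The code is not binding.** It is labelled a reduced example, and it already departs from the imputation model in SAP 14.1.4: it omits type of MS, prior relapses and compliance, and uses weight where the text lists BMI. This stands, so the point applies only if the pooling step is carried over as written. But that step is otherwise complete, and nothing in SAP 14.1.4 would prompt a programmer to add the option.

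**Imputation may never be used.** It is only to be considered, and SAP 14.1.1 analyses early discontinuers on the follow-up they have. This also stands. The ARR is missing only if the relapse count or the time on study is missing. That can still happen: under SAP 14.1.1 an uncollected relapse question at Visit 3 or Visit 6 leaves a count missing.

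**N may be large enough to make this negligible.** It may. SAP 8.2 expects many centres with few patients each, but gives no total.

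**No decision depends on it.** The study is single-arm estimation, and SAP 9 calls all tests exploratory. That supports a low ranking.

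**Stronger readings that do not hold**
- A reader might infer that imputation ought to widen the interval, so that any narrowing shows an error. It need not: valid imputation can recover information relative to the patients with observed ARR.
- A reader might infer that the coded critical value is always below t(N-1). It is not: at λ = 0.50 and N = 100 it is 1.992 against 1.984, and at λ = 0.30 and N = 300 it is 1.971 against 1.968. Only the comparison with Barnard-Rubin degrees of freedom keeps its direction at every N and λ tried.
- A reader might infer that this CI is the plan's only expression of uncertainty about the ARR. SAP 14.1.1 also reports SD and quartiles, and SAP 14.1.2 reports model-based CIs.

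**Conclusion.** The point holds as a minor correction, conditional on imputation being used and the example's pooling step being followed. The pooled 95% CI is then too narrow by about 5% at N=30, 3.5-4% at N=40, 1.7-2% at N=80, 1.3-1.6% at N=100 and under 1% at N of 200 or more. These sizes rest on 6-20% missing information, 20 imputations, the software defaults named above, and an N that the available text does not show.

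This is not a defect in the non-imputed primary analysis. Nor does correcting it bring coverage to 95% when relapse counts are skewed.

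**What to change.** In SAP 18, add to the PROC MIANALYZE statement `edf=` set to the number of FAS patients in each imputed data set minus 1. The preceding PROC MEANS step already writes that count to its output data set. In SAP 14.1.4, add one clause saying that the pooled CI uses these small-sample adjusted degrees of freedom, so that the rule does not depend on example code.

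The cost is one option and one clause, with no new data or analysis. The interval becomes wider by about 5-6% at N=30, 1.3-1.6% at N=100 and under 1% at N of 200 or more.
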